6.2. Secondary Endpoint(s)

6.2.1. Additional Plasma PK parameters of PF-06882961

$C_{\max,u}$, $AUC_{\text{inf},u}$, $AUC_{\text{last},u}$, CL/F , CL_u/F , V_z/F , $V_{z,u}/F$, T_{\max} , $t_{1/2}$ will be listed, summarized descriptively and analyzed by group in the PK parameter set (as defined in Section 4). Missing values will be handled as detailed in Section 5.3.

The additional plasma PK parameters of PF-06882961 for each group will be summarized as specified in Table 8 below.

Table 8. Summary statistics to be produced for Additional Plasma PK Parameters of PF-06882961

Parameter	Summary Statistics
$C_{\max,u}$, $AUC_{\text{inf},u}$, $AUC_{\text{last},u}$, CL/F , CL_u/F , V_z/F , $V_{z,u}/F$	N, arithmetic mean, median, $cv\%$, standard deviation, minimum, maximum, geometric mean and geometric $cv\%$.
T_{\max}	N, median, minimum, maximum.
$t_{1/2}$	N, arithmetic mean, median, $cv\%$, standard deviation, minimum, maximum.

The following plot will be presented:

- Box and whisker plots for individual PK parameters ($AUC_{\text{inf},u}$, $AUC_{\text{last},u}$ and $C_{\max,u}$) will be constructed by group and overlaid with geometric means.

The following summaries will additionally be presented for the plasma concentration data of PF-06882961 using the PK Concentration Set (as defined in Section 4):

- a listing of all concentrations sorted by participant ID and nominal time post-dose for each group. The concentration listing will also include the actual times. Deviations from the nominal time will be given in a separate listing.

- a summary of concentrations for each nominal time post-dose (produced separately for each group), where the set of statistics will include n, mean, median, standard deviation, coefficient of variation (cv), minimum, maximum and the number of concentrations above the lower limit of quantification.
- median concentration time plots (on both linear and semi-log scales) against nominal time post-dose by group in the same plot.
- individual concentration time plots by group (on both linear and semi-log scales) against actual time post-dose (there will be separate spaghetti plots for each group, with a line for each participant, per scale).

The nominal PK sampling time will be used for summary statistics and relevant median plots, whereas for individual participant plots by time, the actual PK sampling time will be used.

6.2.2. Safety Endpoints

Any clinical laboratory, ECG, BP, and pulse rate abnormalities of potential clinical concern will be described.

No formal analyses are planned for safety data.

The safety endpoints detailed in Section 3.2.2 will be listed and summarized in accordance with sponsor reporting standards based on the safety population (as defined in Section 4), with more details provided below.

6.2.2.1. Adverse Events

Adverse events will be summarised by group and overall, in accordance with sponsor reporting standards using the safety population defined in Section 4.

If applicable, subject discontinuations due to adverse events will be detailed and summarized.

6.2.2.2. Laboratory Data

Laboratory data will be listed and summarized by group and overall, in accordance with the sponsor reporting standards using the safety population defined in Section 4. Baseline is as defined in Section 3.2.2.

6.2.2.3. Vital Signs

Absolute values and changes from baseline in supine systolic and diastolic blood pressure and pulse rate will be summarised by group, according to sponsor reporting standards using the safety population defined in Section 4. Baseline is as defined in Section 3.2.2.

Maximum and minimum absolute values and maximum changes from baseline for supine vital signs will also be summarised descriptively by group using categories as defined in Appendix 2. Numbers and percentages of participants meeting the categorical criteria will be provided. All planned and unplanned post dose time points will be counted in these

categorical summaries. All values meeting the criteria of potential clinical concern will be listed.

6.2.2.4. ECG

Absolute values and changes from baseline in QT interval, heart rate, QTcF interval, PR interval and QRS interval will be summarised by group using sponsor reporting standards using the safety population defined in Section 4. Tables will be paged by parameter. Baseline is as defined in Section 3.2.2.

Maximum absolute values and changes from baseline for QTcF interval, PR interval and QRS interval will also be summarised descriptively by group using categories as defined in Appendix 2. Numbers and percentages of participants meeting the categorical criteria will be provided. All planned and unplanned post dose timepoints will be counted in these categorical summaries. All values meeting the criteria of potential clinical concern will be listed.

6.3. Other Endpoint(s)

6.3.1. Urine PK Parameters: CL_r, Ae₂₄, Ae_{24%}

Urine CL_r, Ae₂₄, Ae_{24%} will be listed and summarized descriptively by group for participants in the Urine PK parameter set (as defined in Section 4). Missing values will be handled as detailed in Section 5.3.

The urine PK parameters of PF-06882961 for each group will be summarized as specified in Table 9 below.

Table 9. Summary statistics to be produced for Urine PK Parameters

Parameter	Summary Statistics
CL _r , Ae ₂₄ , Ae _{24%}	N, arithmetic mean, median, cv%, standard deviation, minimum, maximum, geometric mean and geometric cv%.

The following summaries will additionally be presented:

- a listing of all urine concentrations over each time interval sorted by group, subject ID and nominal collection duration postdose.
- listing of all urine PK parameters sorted by group, subject ID and nominal collection duration postdose.

6.3.2. CP-I concentration

CP-I will be summarized descriptively by group and overall for participants in the CP-I concentration set (as defined in Section 4). Missing values will be handled as detailed in Section 5.3.

Linear regression will be used to characterize the potential relationship between appropriate PK parameters (AUC_{inf} [as data permit], $AUC_{inf,u}$ [as data permit], AUC_{last} , $AUC_{last,u}$, CL/F and $CL_{u/F}$) for PF-06882961 versus innate OATP activity (as measured by CP-I on Day 1) as described in Section 5.2.4, where the PK parameter will be the dependent variable in the separate models and CP-I will be the explanatory variable. This will be applied to participants from the T2DM groups only.

Plots of PK parameters vs. CP-I will be constructed separately for each PK parameter. A regression line and 90% confidence region for the PK parameters will be included in the plots and different symbols will be used to identify participants from different renal function groups.

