3. OBJECTIVES AND ENDPOINTS

Objectives	Endpoints
Primary:	Primary:

To compare the PK of PF-06882961 following administration of a single oral dose in adult participants with T2DM and varying degrees of renal impairment relative to T2DM participants without renal impairment.	
Plasma: C_{max}, AUC_{inf}, AUC_{last}, fu, as data permit.
Secondary:	Secondary:

To compare additional PK parameters of PF-06882961 following administration of a single oral dose in adult participants with T2DM and varying degrees of renal impairment relative to T2DM participants without renal impairment.To evaluate the safety and tolerability of a single oral dose of PF-06882961 in T2DM participants with varying degrees of renal impairment and in participants with normal renal function.	
Plasma: $C_{max,u}$, $AUC_{inf,u}$, $AUC_{last,u}$, CL/F, CL_u/F, V_z/F, $V_{z,u}/F$, T_{max}, $t_{1/2}$, as data permit.Incidence and severity of treatment-emergent AEs, clinical laboratory abnormalities, vital signs (blood pressure and pulse rate), ECG parameters (heart rate, QT, QTcF, PR and QRS intervals).
Tertiary/Exploratory:	Tertiary/Exploratory:

To compare urine PK parameters of PF-06882961 following administration of a single oral dose in adult participants with T2DM and varying degrees of renal impairment relative to T2DM participants without renal impairment.To compare the PK of PF-06882961 following administration of a single oral dose in adult participants with T2DM and normal renal function relative to healthy participants with normal renal function.To explore the relationship of markers of innate OATP activity in adult participants with T2DM and varying degrees of renal impairment relative to participants with normal renal function.To enable exploratory research through collection of banked biospecimens, unless prohibited by local regulations or ethics committee decision.	
Urine: CL_r, Ae_{24}, $Ae_{24}\%$.Plasma: C_{max}, T_{max}, AUC_{inf}, AUC_{last}, CL/F, V_z/F, $t_{1/2}$, fu, as data permit;Urine: CL_r, Ae_{24}, $Ae_{24}\%$.CP-I concentration.Potential results from exploratory analysis of banked biospecimens (these results may or may not be generated in the context of the present study).

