Based on the draft FDA Guidance for Industry, plasma and urine samples will be analyzed for PF-06882961. As PF-06882961 was observed to have a $t_{1/2}$ of approximately 4-8 hours, plasma sampling up to 48 hours will be collected. Since PF-06882961 is highly protein bound, to assess the in vivo protein binding of PF-06882961 with varying degrees of renal impairment, the fraction unbound (fu) of PF-06882961 will be determined at approximately the expected T_{max} in each participant. To explore the relationship between OATP activity and CKD, the endogenous biomarker, coproporphyrin I (CP-I), will be measured prior to dosing. CP-I has been reported to be a potential marker of OATP activity. In this study, a single dose of PF-06882961 will be administered with a standard breakfast to reflect the conditions for anticipated use of PF-06882961 in the target T2DM population. Additionally, in study C3421001 in healthy participants, variability based on geometric %CV for C_{max} was lower following administration with a high-fat meal (23% in the fed state, compared to 91% in the fasted state). The adjusted geometric mean C_{max} was 57% lower (90% CI: 28%, 74%) in the fed state compared to the fasted state, while mean AUC_{inf} values were similar (approximately 12% lower in the fed state [90% CI: -5%, 26%]).

While GLP-1R agonists typically are not associated with hypoglycemia unless co-administered with anti-diabetic agents that can cause hypoglycemia (such as insulin or sulfonylureas), blood glucose concentrations will be monitored throughout the study via glucometer, and monitoring of symptomatic HAEs will be performed. As is typical for studies with renally impaired participants, vital signs will be obtained in the seated position. In addition, COVID-19 specific assessments have been incorporated to minimize the risks of COVID-19 related complications to participants and the study site personnel.

Both females of childbearing potential as well as those who are of non-childbearing potential will be enrolled given the availability of embryo fetal developmental (EFD) toxicity studies with PF-06882961. However, as marketed GLP-1R agonists are listed as contraindicated in pregnancy, measures will be taken to limit the risk of pregnancy in the female population enrolled (see [SoA](#) and [Section 10.4](#)).

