5.2.4. Linear Regression

Linear regression analysis will include eGFR as the explanatory variable, based on eGFR values obtained on Day 1 and will include only participants from the T2DM groups (Groups 2 to 5). Estimates of the slope and intercept, together with their precision (90% CIs), and the coefficient of determination will be obtained from the model. Example SAS code is given in [Appendix 1](#).

Additionally, as an exploratory analysis, the effect of weight, gender and age will be explored as additional covariate/factors in the models, as appropriate. This will be implemented by utilizing a stepwise linear regression approach, with model selection using Akaike's Information Criterion [AIC]). All the above covariates and factors will be considered (eGFR will be restricted to always remain in the model) and if the final model selected includes at least one of these additional covariates/factors, this additional model will be reported in addition to the main linear regression above. Example SAS code is given in [Appendix 1](#).

5.3. Methods to Manage Missing Data.

For the analysis of safety endpoints, the sponsor data standard rules for imputation will be applied.

In all PK data presentations (except listings) and CP-I, concentrations below the limit of quantification (BLQ) will be set to zero. In listings BLQ values will be reported as “<LLQ”, where LLQ will be replaced with the value for the lower limit of quantification.

In PK summary tables and plots of median profiles, statistics will be calculated having set concentrations to missing if one of the following cases is true:

1. A concentration has been collected as ND (i.e. not done) or NS (i.e. no sample),
2. A deviation in sampling time is of sufficient concern or a concentration has been flagged anomalous by the pharmacokineticist.

Note that summary statistics will not be presented at a particular time point if more than 50% of the data are missing.

Participants who experience events that may affect their PK profile (e.g. lack of compliance with dosing or vomiting) may be excluded from the PK analysis. At the discretion of the pharmacokineticist, a concentration value may also be excluded if the deviation in sampling time is of sufficient concern or if the concentration is anomalous for any other reason.

A full list of protocol deviations will be compiled and reviewed to identify major and minor deviations prior to database closure.

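### CP-I is only described by renal group, with no ratio, interval or eGFR model, and the one planned CP-I model (PK on CP-I) cannot separate OATP activity from other effects of renal impairment

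*SAP*

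**What the plan says.** The Protocol objectives table (Section 3, repeated in SAP 2.1) includes an exploratory aim that begins "To explore the relationship of markers of innate OATP activity in adult participants with T2DM and varying degrees of renal impairment", with normal renal function as the comparator and CP-I concentration as the endpoint. Protocol 4.2 gives the reason for the sample: "To explore the relationship between OATP activity and CKD, the endogenous biomarker, coproporphyrin I (CP-I), will be measured prior to dosing".

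SAP 6.3.2 plans three things for CP-I:

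- A summary: "CP-I will be summarized descriptively by group and overall for participants in the CP-I concentration set".
- Linear regressions of AUCinf, AUCinf,u, AUClast, AUClast,u, CL/F and CLu/F on CP-I, carried out as in Section 5.2.4, "where the PK parameter will be the dependent variable in the separate models and CP-I will be the explanatory variable". On the population: "This will be applied to participants from the T2DM groups only".
- Plots of each PK parameter against CP-I, in which "different symbols will be used to identify participants from different renal function groups".

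Section 5.2.4, to which 6.3.2 refers, is written for a different predictor: "Linear regression analysis will include eGFR as the explanatory variable, based on eGFR values obtained on Day 1". Its stepwise step considers weight, gender and age, and there "eGFR will be restricted to always remain in the model". The ANOVA parameter lists in Protocol 9.4.3.1.3 and SAP 6.1.1.1 do not include CP-I.

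**The concern.** The question asked is CP-I against renal function. The question modelled is PK against CP-I. The first gets group summaries but no effect estimate with an interval. The second pools participants from normal renal function to dialysis.

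Protocol 4.2 itself says that renal impairment may change metabolism and transport in other organs, including for OATP substrates. So CP-I and clearance could both move with renal function. A slope of PK on CP-I would then carry whatever renal impairment does to clearance by any route, and a reader could take all of it for OATP activity. What is at stake is the interpretation of an exploratory biomarker.

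**Working it through.** **1. The plan's own figure.** No precision figure is given for CP-I. The only design figure is the ±0.490 half-width in Protocol 9.2, for log AUCinf or Cmax. With SD 0.489, n = 8 per group and 14 degrees of freedom:

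t(0.95, 14) × SD × √(2/n) × √(χ²(0.80, 14)/14) = 1.761 × 0.489 × 0.5 × √(18.151/14) = 0.490.

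It reproduces, and this point does not affect it.

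**2. Does the reference to 5.2.4 bring eGFR in?** Three readings are possible.

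- CP-I replaces eGFR throughout, including as the forced term. Then eGFR never enters.
- CP-I replaces eGFR in the main model, but eGFR stays forced in the stepwise step. Then eGFR appears only in the stepwise model, which is reported only if weight, gender or age is selected.
- CP-I is added to eGFR in the main model. This does not fit 6.3.2, which names CP-I as the explanatory variable.

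The first two fit the text, and neither guarantees an eGFR-adjusted CP-I slope.

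**3. What a shared renal dependence could do.** If CP-I correlates a with eGFR, log PK correlates b with eGFR, and CP-I has no direct effect on PK, the correlation of CP-I with PK is a × b. The values of a and b are assumptions. The regression has 32 participants, or 30 if Group 5 has 6. The table shows how often the 90% interval for the CP-I slope excludes zero (20,000 simulated trials per row; nominal 10%).

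| Size of a and b | a × b | N = 32, CP-I only | N = 30, CP-I only | eGFR added |
|---|---|---|---|---|
| 0 | 0 | 10% | 10% | 10% |
| 0.3 | 0.09 | 14% | 14% | 10% |
| 0.5 | 0.25 | 40% | 38% | 10% |
| 0.6 | 0.36 | 66% | 64% | 10% |
| 0.7 | 0.49 | 90% | 88% | 10% |

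A second version follows the group structure: 8 per group, eGFR centred at 105, 75, 45 and 15, and PK SD 0.489. Exposure rises 2-fold from normal to severe, the rise that Protocol 4.3 contemplates for tolerability. The CP-I rise (1.5-, 2- or 3-fold) and the log CP-I SD are assumed.

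- Log CP-I SD 0.3: 34%, 59% and 77% with CP-I only.
- Log CP-I SD 0.489: 21%, 36% and 57% with CP-I only.
- With eGFR added: about 10% throughout.
- If exposure or CP-I does not change with eGFR: 10% with or without eGFR.

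**4. The opposite case: OATP as the path from renal impairment to PK.** Assume a true slope of 0.3 per SD of OATP activity, total PK SD 0.489, and OATP activity correlated ρ with eGFR. If CP-I is a perfect marker, both slopes average 0.30; at ρ = 0.7 the standard error rises from 0.070 to 0.100 on adding eGFR. If CP-I has reliability 0.5:

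- Unadjusted slope: 0.3 × 0.5 = 0.15.
- Adjusted slope: 0.3 × (1 − ρ²)/(2 − ρ²). At ρ = 0.3 this is 0.3 × 0.91/1.91 = 0.143; at ρ = 0.7 it is 0.3 × 0.51/1.51 = 0.101.
- By simulation with N = 32, the chance that the 90% interval excludes zero falls from about 82% to about 76% at ρ = 0.3 and about 46% at ρ = 0.7.

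Adjustment protects against one misreading and can hide a real effect in the other.

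**The case against.** The strongest reply is that the plan is adequate for what it claims. The objective says explore, where the PK objectives say compare. The study has no hypothesis tests and no decision rules. CP-I is summarised by group with N, mean and SD, so the comparison can be read and its precision judged roughly. The regression is meant to characterise a potential relationship, and an unadjusted slope does that; no causal claim is planned. Renal groups carry different plot symbols, and CL/F and CLu/F are also regressed on eGFR in SAP 6.1.1.1, so a reader sees both relations. Protocol 4.2 also fits OATP as a mediator, and with urinary recovery below 0.1% of dose (Protocol 2.2.4.2) renal excretion can hardly drive exposure.

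Much of this stands. A reader might infer that the stated relationship is ignored, or that the PK slope is simply confounded and wrong. The documents support neither: the group comparison is described, and the slope is a valid marginal association. Low urinary recovery does not settle the matter, because renal impairment could alter clearance through metabolism or protein binding as well as through OATP. What remains is that the stated question gets no estimate with an interval, and that the reference to 5.2.4 is unclear.

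**Conclusion.** The point holds as a low-cost improvement to an exploratory analysis. CP-I against renal function is described by group but not estimated, and the one CP-I model cannot separate OATP activity from other renal effects on clearance.

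The 14% to 90% range shows the mechanism; it does not predict this trial. It rests on assumed correlations of 0.3 to 0.7 and on no direct CP-I effect, and the documents give neither these correlations nor a CP-I variance. The 2-fold exposure rise is a tolerability contingency, not an expected effect. It would also be too strong to infer that the eGFR-adjusted slope is the correct one: where OATP is a mediator and CP-I a noisy marker of it, that slope is attenuated. No primary or secondary result changes.

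**What to change.** In SAP 6.3.2:

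1. Apply the ANOVA of 5.2.3 to ln(CP-I) and report geometric mean ratios for Groups 3, 4 and 5 against Group 2 with 90% CIs.
2. Regress ln(CP-I) on Day 1 eGFR in Groups 2 to 5 by the method of 5.2.4, with slope, 90% CI and coefficient of determination.
3. Keep the unadjusted slopes of PK on CP-I. Show an eGFR-adjusted slope beside each one as a sensitivity analysis only. State whether the forced eGFR term and the stepwise covariates of 5.2.4 apply.
4. Add a rule for CP-I values below the limit of quantification. SAP 5.3 sets them to zero, which has no logarithm.

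No new data are needed, only SAP text and small additions to existing code. The ratios will be imprecise. By the formula in step 1 of the working, the half-width is 0.490 if the log CP-I SD is 0.489 (a factor of 1.63 either way), or 0.490 × 0.3/0.489 = 0.301 if it is 0.3 (a factor of 1.35). The adjusted PK slopes will have wider intervals and may be attenuated, so the text should say that the two slopes answer different questions.

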6.4. Subset Analyses

No subset analyses will be performed.

6.5. Baseline and Other Summaries and Analyses

Data will be reported in accordance with the sponsor reporting standards.

6.5.1. Baseline Summaries

Demographics data (age, biological sex, race, ethnicity, weight, body mass index and height) will be summarized by group and overall, as outlined in Sections 5.2.1 and 5.2.2 as applicable.

6.5.2. Study Conduct and Participant Disposition

Participant evaluation groups will show end of study participant disposition by group and will show which participants were analyzed for pharmacokinetics (plasma and urine, separately), PD and safety, which may not be produced in one table. Frequency counts and percentages will be supplied for participant discontinuation(s) by group.

6.5.3. Concomitant Medications and Nondrug Treatments

All prior and concomitant medication(s) as well as non-drug treatment(s) will be provided in listings.

6.5.4. Other Screening Data

These data will not be recorded in the study database, and therefore will not be listed.

6.6. Safety Summaries and Analyses

See Section 6.2.2.

7. INTERIM ANALYSES

7.1. Introduction

No formal interim analysis will be conducted for this study. As this is an open-label study, the sponsor may conduct unblinded reviews of the data during the course of the study for the purpose of safety assessment, facilitating PK/PD modeling, and/or supporting clinical development.

7.2. Interim Analyses and Summaries

Not applicable.

9. APPENDICES

Appendix 1. Statistical Methodology Details

An example of SAS code for ANOVA:

```
proc mixed data = tab.pk;
  class group;
  model l&var = group /residual;
  lsmeans group/diff cl alpha=0.1;
  ods output lsmeans = lsmeans&var;
  ods output diffs=diffs&var;
run;
```

An example of SAS code for the PROC REG code for linear regression analyses:

```
proc reg data=tab.pk;
  model l&var=clcr/clb alpha=0.1;
  ods output ParameterEstimates = param&var;
  ods output FitStatistics = fit&var;
  ods output ANOVA = reg&var;
run;
```

An example of SAS code for stepwise regression with model selection using AIC:

```
proc glmselect data=tab.pk analysis plot=ALL;
  class gender;
  model pk_p = eGFR_cg age gender weight/ selection=stepwise (select = AIC stop = AIC)
    include=1 hierarchy=none showpvalues;
run;
```

